PROTOCOL and SAP

The Role of Human Fibrinogen Concentrate (RiaSTAP) in Decreasing Blood Loss and the Need for Component Blood Therapy in Infants Undergoing Cardiopulmonary Bypass

National Clinical Trial (NCT) Identification Number: NCT02822599

December 7, 2017

Purpose of Study

The goal of the study is to determine whether the use of Human Fibrinogen Concentrate (RiaSTAP) will decrease blood loss and the need for component blood therapy in neonates and infants undergoing cardiopulmonary bypass. RiaSTAP will be administered after termination of Cardiopulmonary Bypass (CPB) at a dose of 70 mg/kg, in a prospective, randomized, controlled study. We hypothesize that the administration of RiaSTAP in this manner will reduce peri-operative bleeding and transfusion requirements.

Background

Severe postoperative bleeding is a serious complication after cardiac surgery and results in increased morbidity and mortality¹². The bleeding is often multifactorial and influenced by both surgical factors and impaired hemostasis. The impaired hemostasis after cardiac surgery may be caused by enhanced fibrinolysis, platelet (PLT) dysfunction and coagulopathy secondary to the exposure of blood to artificial surfaces, and the surgical trauma³.

In children less than 12 months old with congenital heart disease, bleeding after cardiac surgery is further complicated as the fibrinogen of these patients is qualitatively dysfunctional⁴. Moreover, the coagulation systems of neonates and children undergoing CPB are profoundly affected by hemodilution⁵ and by consumption⁶. As a result, neonates and young infants undergoing complex cardiac repairs often receive multiple units of blood products, both in the operating room (OR) and intensive care unit (ICU).

Preoperative fibrinogen concentration is an independent predictor of post-operative bleeding volume. Fibrinogen concentration, even when within the normal range, is a limiting factor for post-operative hemorrhage⁷. The prophylactic infusion of fibrinogen concentrate has been shown to reduce bleeding after coronary artery bypass graft (CABG) surgery without evidence of hypercoagulability⁸. Moreover, ROTEM FIBTEM test guided fibrinogen concentrate administration was associated with reduced transfusion requirements and 24 hour postoperative bleeding in patients undergoing aortic valve operations and ascending aortic reconstructions⁹.

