Our institution has been using RiaSTAP on this high-risk patient population since April 2013. In a separate, retrospective analysis our group has compared a group of 50 patients who received RiaSTAP with 50 age, diagnosis and procedure matched patients prior to April 2013. Our analysis demonstrates that there is a statistically significant reduction in the need for FFP and cryoprecipitate, without an increase in thromboembolic events, when RiaSTAP is used at a dose of 70 mg/kg.¹⁵

Criteria For Subject Selection

Number of subjects: 30

Gender of subjects: There are no gender-based enrollment restrictions for this study. Gender distribution should reflect the gender distribution of the patient population and the gender distribution of Congenital Heart Disease (CHD) in general which is slightly skewed towards male patients in a 60:40 ratio of males to females.

Age of Subjects: Age will range from full term (at least 37 weeks gestational age) newborns to 12 months old, inclusive.

Racial and Ethnic Origin: There are no racial and ethnic restrictions for this study.

Inclusion Criteria: All neonatal and infant cardiac patients presenting for open-heart surgery at Nicklaus Children's Hospital will be eligible for enrollment in the study.

Exclusion criteria: Patients who fall outside of the age range for the study will be excluded. Patients known to have had an anaphylactic or severe reaction to the drug or its components will not be enrolled. At the time of the rewarming ROTEM, any patient with a FIBTEM MCF > 15 mm, will be excluded.

Vulnerable subjects: Patients in the study population are neonatal and infant cardiac surgical patients and are considered vulnerable subjects.

Methods and Procedures

Randomization:

We plan to enroll 30 neonates and infants scheduled for elective cardiac surgery. Patients will be randomized to one of two groups with 15 patients in each group; Group 1 will receive an infusion of RiaSTAP, right after the termination of CPB at a dose of 70 mg/kg and

Group 2 will receive a placebo of Normal Saline 0.9% (NS) during the same time period. The volume of NS will be calculated to be the same volume that would be used IF the patient were receiving RiaSTAP. This will be the only difference between the groups.

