Both Groups will receive the normal standard of care both before and especially after this event. This will be the only event that is different for the two groups. To avoid selection bias, the Pharmacy will perform the randomization using Research Randomizer. Briefly, for each patient, a randomly generated integer between 1-30 will be produced. If the number is even, the patient will be assigned to Group 1. If the number is odd, the patient will be assigned to Group 2. The randomization process and schedule will be provided by the Principal Investigator's office, but the actual patient assignment will be done by Pharmacy.

All operating room and ICU personnel will be blinded to the patient's Group assignment. The only persons who will have access to the identity of the Group assignment from the time of randomization until 24 hours after surgery will be members of the Pharmacy staff. NONE of these individuals will be involved in patient care. The DSMB will be unblinded AFTER the study treatment period concludes (24 hours after surgery).

Endpoints:

Primary efficacy endpoints will be estimated as follows:

- postoperative bleeding (EBL) during the first 24 hours (hr) after surgery (cc/kg),
- the identity and total volume of transfused blood products (cc/kg) given in the peri-operative period, separated out into its components,
- hemoglobin concentration 2 hr. and 24 hr. after surgery and
- effects of fibrinogen infusion on global hemostasis 2 hr. and 24 hr. after surgery (PT, PTT, INR, fibrinogen level, platelet count and ROTEM analysis).

Post-operative period begins after the patient leaves the operating room. The need for Factor VII use and dose will also be included as a primary end point. Factor VII is typically used only if there is profuse bleeding not amenable to component transfusion therapy.

Secondary end points will include:

- the number of post-op hours requiring ventilator support,
- Length of Stay (LOSH) in the hospital,
- Length of Stay (LOS ICU) in the Cardiac Intensive Care Unit (CICU) and
- the need for re-exploration for bleeding within the first 12 hours.

The primary safety endpoints that will be monitored are the presence of a clinical adverse events. Clinical adverse events (AEs) are defined as any clinical signs of central or peripheral thromboembolism, respiratory or circulatory failure, or allergic reactions during hospital stay. It will also include infection with a blood-borne pathogen.

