To avoid selection bias, patients will be randomized to their treatment assignment group by the research pharmacists using the Research Randomizer. The randomization procedures are detailed in the Methods and Procedures section of this protocol. All operating room and ICU personnel will be blinded to the patient's Group assignment. An intensive care nurse blinded to group assignment will record postoperative bleeding every hour. Since the study is blinded and the practitioners caring for the patient will not know if the subject received the study drug or placebo, for the study treatment period (ending 24 hours after surgery), the Cardiac Intensive Care Unit staff will monitor the incidence of adverse thromboembolic events and intervene with routine care, if necessary. In order to maintain patient safety, the ROTEM analyses must be interpreted by the anesthesiologist caring for the patient in order to guide transfusion therapy. This is the standard of care and an integral part of the protocol. The hospital staff anesthesiologists are also investigators in the study including the Principal Investigator. As part of routine care, if the ROTEM results indicate a deficiency of platelets or FFP, either component will be administered while still in the OR. In addition, if the ROTEM indicates a fibrinogen deficiency after termination of CPB, cryoprecipitate will be given. After review of the ROTEM values, the identity of the study drug may be discernable. In order to avoid the ascertainment bias from this knowledge, study data will be analyzed by a biostatistician independent of the investigator prior to any presentation or publication of study results. The biostatistician will be blinded to the study treatment assignment.

Statistical Analyses

All quantitative measures will be analyzed using descriptive statistics [mean +/- standard deviation (SD), etc.]. Treatment and placebo group comparisons will be made with the Student's t-test (continuous variables) or Fisher's exact test (categorical variables). A p-value of ≤ 0.05 will be considered statistically significant. For group comparisons of variables that will be analyzed at more than onetime point, Analysis of Variance (ANOVA) for repeated measurements will be used followed by Student's t-test if the ANOVA (group or interaction between group and time) indicated a statistically significant difference ($p \leq 0.05$).

Data Storage and Confidentiality

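### Ventilator hours, CICU stay and hospital stay are compared by t-test with no provision for death, so an early death either enters as a short, favourable time or drops out of the comparison

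*Combined protocol and SAP*

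**What the plan says.** The Endpoints section of the combined protocol and SAP lists four secondary endpoints. Three are plain durations: "the number of post-op hours requiring ventilator support", "Length of Stay (LOSH) in the hospital" and "Length of Stay (LOS ICU) in the Cardiac Intensive Care Unit (CICU"). The fourth is re-exploration for bleeding within 12 hours. The Patient Assessment section repeats the three durations without further definition.

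The Statistical Analyses section has one general rule for such variables: "Treatment and placebo group comparisons will be made with the Student's t-test (continuous variables"). Summaries are mean and SD, and "A p-value of ≤ 0.05 will be considered statistically significant". That section makes no mention of death.

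Elsewhere, death is not listed as an efficacy or safety endpoint. The nearest item is circulatory failure, which Patient Assessment defines as cardiac arrest. Mortality appears only in the Background: "Severe postoperative bleeding is a serious complication after cardiac surgery and results in increased morbidity and mortality". No rate is given.

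**The concern.** For each of these durations a shorter time is read as a better outcome. An infant who dies soon after surgery accrues few ventilator hours and few days in the CICU and hospital. If those times go into the t-test as recorded, the worst outcome in the trial improves its own arm's mean on three of the four secondary endpoints. A death in the treated arm would then push these endpoints towards benefit, and a death in the control arm would push them against the drug.

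Leaving deaths out is the other obvious choice. It restricts the comparison to survivors, a group defined after randomisation, so the arms are no longer protected by the randomisation. The plan chooses neither option. With 15 infants intended per arm, a choice made after the data are seen would be open to challenge.

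**Working it through.** **Inputs from the documents.** "Number of subjects: 30", with 15 intended per group; a t-test on continuous variables; a 0.05 threshold, sidedness not stated. The plan gives no figure for mortality, ventilator hours or length of stay, so there is no planned value to reproduce. Everything below that depends on those quantities is an assumption.

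**Step 1. Shift in an arm mean from early deaths.** Suppose k of 15 infants die at time t and the others have mean M. The arm mean changes by −k × (M − t)/15.

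Hospital or CICU stay, death on day 1 (t = 1), one death:

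| Assumed M (days) | Change (days) | Relative change |
|---|---|---|
| 7 | −6/15 = −0.40 | −5.7% |
| 14 | −13/15 = −0.87 | −6.2% |
| 21 | −20/15 = −1.33 | −6.3% |
| 30 | −29/15 = −1.93 | −6.4% |

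Two such deaths double each change, to between −0.8 and −3.9 days (11% to 13%).

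Ventilator hours, one death at 12 hours: with M = 24 the change is −12/15 = −0.8 hours (3.3%); with M = 168 it is −156/15 = −10.4 hours (6.2%).

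The formula also shows the limit of the argument. The change is negative only when t is below M, so a death after a long stay raises the mean.

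**Step 2. Effect on the planned test.** Assume log-normal stays with median 10 days and log-SD 0.8, no true treatment effect, and day-1 deaths falling on random infants in the control arm. In simulation, one death shifts the difference in means by about 0.86 day. The SD of that difference is about 4.7 days, so the shift is 0.86/4.7 = 0.18 standard errors. Overall rejection by a two-sided t-test stays at about 4%. Significant results in favour of control go from about 2% with no death to about 3% with one and about 5% with two. With two deaths the control mean is the lower one in about 65% of trials, against 50% without deaths; that figure counts only the sign of the difference.

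**Step 3. How often deaths might arise.** The chance of at least one death among 30 is 1 − (1 − m)^30. The chance of two or more in an arm of 15 is 1 − (1 − m)^15 − 15m(1 − m)^14.

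| Assumed mortality m | At least 1 in 30 | At least 2 in one given arm |
|---|---|---|
| 1% | 26% | 1% |
| 3% | 60% | 7% |
| 5% | 79% | 17% |
| 10% | 96% | 45% |

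Both columns count deaths at any time during the hospital stay. Early deaths are a subset.

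**Step 4. What worst-rank scoring does.** Take two identical arms with made-up stays of 5, 6, 7, 7, 8, 9, 10, 11, 12, 14, 16, 20, 25, 30 and 40 days (mean 14.7, median 11). In arm A, replace the 40-day infant by a death on day 1. On raw times, arm A's mean falls to 12.1, its median to 10, and the mean ranks are 14.5 for A and 16.5 for B, so the arm with the death looks better. With the death ranked worst, the mean ranks are 15.5 and 15.5, and the apparent advantage is gone. Moving to a rank test without re-scoring the death would not have removed it.

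**The case against.** The strongest objection is that the plan contains no rule that scores death as a good outcome. A reader might infer one from the t-test sentence, but that sentence is a generic provision for all continuous variables and is silent on death. Using the truncated time, analysing survivors only and treating the value as missing are all compatible with it. This stands: the gap is an omission, and favourable scoring of an early death is only what follows if raw times are used.

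A reader might also infer from the Background that deaths must be related to arm, because bleeding is both the treatment target and a stated cause of mortality. The documents do not support that step. They give no infant mortality rate and no mortality difference by treatment, and the planned surgery is elective. The drug's listed thrombotic risks make an effect in the other direction conceivable too. An imbalance is plausible and no more.

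Third, the chance of at least one death among 30 is not the chance of a misleading result. That needs early deaths concentrated in one arm, and even two day-1 deaths in one arm leave the t-test seldom significant. This also stands.

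Finally, one might read the gap as hiding deaths. That goes too far. Adverse events are followed to discharge and asked about in the 60-day call, cardiac arrest is part of the primary safety endpoint, and safety data are reviewed after 10, 20 and 30 subjects. A death would probably be known. None of this repairs the three duration comparisons, which nothing in the plan links to those safety data.

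**Conclusion.** The point holds as a minor omission on secondary endpoints. Three of the four are durations truncated by death, the specified test takes no account of that, and both ways of filling the silence can bias the comparison. Under the assumed mean stays, one day-1 death moves an arm mean by about 6%, and one death at 12 hours moves mean ventilator hours by about 3% to 6%. Either is unlikely on its own to change significance with 15 per arm. The bias matters more if several early deaths fall in one arm, and not at all if nobody dies. These sizes rest wholly on assumed stays, ventilation times and mortality. The documents support neither a stated rule that rewards death nor a demonstrated link between death and treatment arm.

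**What to change.** Add one sentence to Statistical Analyses: for ventilator hours, CICU stay and hospital stay, infants who die before extubation, CICU discharge or hospital discharge respectively receive the worst rank, arms are compared by the Wilcoxon rank-sum test instead of the t-test, and deaths by arm are reported beside these endpoints. Settle this before unblinding.

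It needs no extra infants, visits or data beyond the date and time of any death. The price is in interpretation: the test addresses a composite of death and duration and yields a rank comparison, not a mean difference in hours or days. Worst rank is not the only defensible choice. Days alive and free of ventilator, CICU or hospital within a fixed window, or time to extubation or discharge with death as a competing event, would also close the gap. Worst rank is the smallest change to the present text.

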Thromboembolic phenomenon will include catheter and/or vessel occlusion. Any signs or symptoms of thromboembolism will prompt a Doppler ultrasound examination to confirm the diagnosis. All patients will be monitored for AEs until discharge.

Anesthetic Management:

Standard non-invasive monitors will be employed including Electrocardiogram (EKG), Non-invasive blood pressure (NIBP), Pulse Oximetry (SaO_2), capnography, and Near Infrared Spectroscopy (NIRS).

For patients greater than six months of age, premedication with midazolam will be used. Dose will be 1 mg/kg Per Os (PO), with a maximum of 20 mg. Anesthesia will be induced with Propofol 2 mg/kg or fentanyl 5 mcg/kg, if the patient already has an indwelling IV catheter. Otherwise an inhalational induction with Sevoflurane 5% will be done. Anesthesia maintenance will be with Sevoflurane and dexmedetomidine 1 mcg/kg/hr. No more than 10 mcg/kg of fentanyl will be used. Once the patient is anesthetized and intubated a Foley catheter will be placed along with an Arterial line (A-line) and a double lumen Central venous line (CVL). Hemodynamics will be maintained by adjusting the Sevoflurane concentration in increments of 0.5% to maintain blood pressure within 20% of baseline. Propofol 0.5 mg/kg will also be used for this purpose.

Cardiopulmonary Bypass (CPB) Management:

After purse strings sutures are placed, heparin 300 International Units (IU) will be administered by the surgeon directly into the right atrium (RA) in order to maintain an ACT greater than 400 seconds. After CPB, the heparin will be reversed by the administration of protamine (1 mg protamine/100 IU of residual heparin activity as measured by the Medtronic Hepcon) to an ACT of <130 s. The CPB circuit included a membrane oxygenator and centrifugal pumps. Standard non-pulsatile CPB technique with moderate hypothermia (bladder temperature 28–30°C) or deep hypothermia (bladder temperature 18–20°C) and hemodilution will be used depending on the surgical repair. Cardioprotection will be achieved with antegrade cold blood cardioplegia. Weaning off CPB will be performed after rewarming to a bladder temperature of at least 36°C. We will use the Medtronic Hepcon Hemostasis Management System Plus to optimize and monitor heparin and protamine dosing.

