Primary efficacy endpoints will be postoperative bleeding during the first 24 hours (hr) after surgery (cc/kg), the total volume and identity of transfused blood products (cc/kg), hemoglobin concentration 2 hr. and 24 hr. after surgery and effects of fibrinogen infusion on global hemostasis 2 hr. and 24 hr. after surgery (PT, PTT, INR, fibrinogen level, platelet count and ROTEM analysis). Secondary end points will include the number of post-op hours requiring ventilator support, Length of Stay (LOS) in the Cardiac Intensive Care Unit (CICU), the need for re-exploration for bleeding within the first 12 hours, and LOS in the hospital. The need for Factor VII use and dose will also be included.

The primary safety endpoint is a clinical adverse event. Clinical adverse events are defined as:

1. Any clinical signs of central or peripheral thromboembolism. This will then be confirmed by Doppler ultrasound. Assessments will be made once per shift (once every eight hours)
2. Respiratory or circulatory failure. Parameters of respiration, like respiratory rate (RR), end-tidal CO₂ (ETCO₂) and circulation, like heart rate (HR), rhythm, blood pressure (BP), arterial oxygen saturation (SpO₂) are monitored continuously while in the ICU. Respiratory failure will be defined as the need for reintubation after extubation. Circulatory failure will be defined as cardiac arrest.
3. Allergic reactions during hospital stay. These will include signs or symptoms like urticaria, wheezing, angioneurotic edema, and anaphylaxis.
4. Infection with a blood borne pathogen. Manifestation of an infection with a blood borne pathogen is unlikely to occur during the study treatment period, which ends 24 hours after the end of surgery. If this were to occur, it would not manifest itself for weeks or even months.

Patients will be assessed once per shift (once every eight hours) for signs of thromboembolism. Any evidence of thromboembolism will warrant a vascular ultrasound to assess the integrity of the vessel.

Adverse events will be monitored until discharge.

All patients will be assessed for signs and symptoms of thromboembolism, per routine care. Specifically, patients will be assessed for signs and symptoms of central and arterial

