All data for the study will be stored on a Nicklaus Children's Hospital password protected computer. Access to the data will be limited to the Investigators and study personnel. All subject identifiers will remain strictly confidential. After the study closure, all consent forms and study data will be kept in a locked cabinet in the Research Institute Clinical Research Coordinators' office at Nicklaus Children's Hospital.

Transition From Research Participation

The study treatment period ends 24 hours after surgery. All patients will be provided routine care within the CICU. A follow-up phone call will be made 60 (± 14) days after the end of the study treatment period.²⁰ Subjects will be asked about any adverse events or

hospitalizations.

We will maintain surveillance for blood borne infections (Cytomegalovirus, HIV, Hepatitis, etc.) by contacting the parents of the study participants and asking them if their child has been diagnosed with any blood borne illness since they took part in the study.

We will also ask if their child received any additional blood products aside from the one received during their participation in the study.

[figure not shown]
We will again provide the parents our study team's contact information and advise them that it is important to notify us if their child develops any of the above referenced illnesses.

Figure 1 ROTEM Assays

ROTEM® Assays

Assay	Indications for Use	Principle	Storage/Stability
ap-tem®	Provides information on clot firmness after breaking hyperfibrinolysis by aprotinin	Plasmin antagonist Aprotinin prevents fibrinolysis in vitro. Evidence of fibrinolytic activity is obtained by comparing the results of ex-tem® and ap-tem®	- Store at +2 - +8°C - Stable until the expiration on label. Vials must be used within 14 days after opening
ex-tem®	Used to monitor the coagulation process via the extrinsic pathway and its interaction with thrombocytes in citrated blood	Reagent contains concentration of tissue factor and phospholipids used for a mild extrinsic activation of the coagulation system	- Store at +2 - +8°C - Stable until the expiration on label. Vials must be used within 8 days after opening

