Potential Risk: According to the manufacturer RiaSTAP is “contraindicated in patients known to have had an anaphylactic or severe reaction to the drug or its components”. “Thrombotic events have been reported in patients receiving RiaSTAP. The most severe adverse reactions observed are thrombotic episodes (pulmonary embolism, myocardial infarction and deep vein thrombosis. The most common adverse reactions observed in clinical studies (frequency > 1%) were fever and headache”. Moreover, “RiaSTAP is made from pooled human plasma. Products made from human plasma may contain infectious agents, i.e., viruses and, theoretically, the Creutzfeldt-Jakob disease (CJD) agent.”

Protection against risks: The patients will be assessed for thromboembolic events at least once per shift. If symptomatic evidence exists that a venous or arterial occlusion has occurred an Ultrasound will be ordered. Assessment for anaphylactic reactions will be made at the time of drug administration by the anesthesiologist. There is no additional surveillance for blood borne infectious agents. As with any patient, bloodborne illnesses will be diagnosed and treated at the time of occurrence.

Potential Benefits to the Subjects: The study drug can potentially decrease blood loss and decrease the need for transfusion therapy.

Alternative to Participation: Usual standard of care will be employed for all patients not participating.

Subject Identification, Recruitment and Consent

Method of Subject Identification and Recruitment

All neonatal and infant patients scheduled for open-heart surgery will be recruited.

Process of Consent

Principal Investigator, Sub-Investigators, Clinical Research Coordinators, and Cardiac Nurse Practitioners will be authorized to obtain consent. No undue coercion will be employed on any potential patients and families to enroll.

Subject Capacity

Since the study patients will be neonates and infants, consent will be obtained from the parents or legal guardian of the child.

Subject/Representative Comprehension

The person obtaining consent will provide a detailed overview of the study protocol to all prospective patients/families. All potential risks and benefits of the study drug will be discussed with the family. All questions will be answered and no enrollment will be allowed unless the study subjects/families have a complete understanding of the protocol.

Consent Forms

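### The plan contradicts itself on whether safety observation ends at discharge or at the 60-day call, and never says which events count in the primary safety endpoint

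*Combined protocol and SAP*

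**What the plan says.** The primary safety endpoint is a clinical adverse event. Its components are thromboembolism, respiratory or circulatory failure, allergic reaction and blood-borne infection.

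- **Endpoints.** The list ends "respiratory or circulatory failure, or allergic reactions during hospital stay". The time limit could apply to the whole list or only to its last item. Infection is added in a separate sentence with no limit: "It will also include infection with a blood-borne pathogen". The same section then says "All patients will be monitored for AEs until discharge".
- **Patient Assessment.** In the numbered list the limit is attached to one component only: "Allergic reactions during hospital stay". On infection the text says "If this were to occur, it would not manifest itself for weeks or even months". The section also states "Adverse events will be monitored until discharge".
- **Schedule of Events.** The Adverse Events row is marked in the 60 ± 14 day column. Note 14 starts reporting at consent and gives no end date.
- **Transition From Research Participation.** "A follow-up phone call will be made 60 (± 14) days after the end of the study treatment period". Families are asked about adverse events, hospitalizations and blood-borne illness, and the text describes this as maintained surveillance. The call is not restricted by arm.
- **Protection against risks.** "There is no additional surveillance for blood borne infectious agents".

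Hospital length of stay is a secondary endpoint. For categorical outcomes, Statistical Analyses names Fisher's exact test and no method based on person-time or time to event.

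**The concern.** Two different windows can be drawn from the same plan, and no sentence chooses between them. A thrombosis diagnosed after discharge and reported at the call could be put in the primary safety endpoint or left out, and that choice could be made after the data are seen.

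The discharge window also has a weakness of its own. Its length is determined after randomization and may depend on treatment. If fibrinogen concentrate shortens hospital stay, the treated infants are observed for less time and will tend to show fewer events at the same true risk. The Safety Team, which consists of the CICU physicians, is no longer blinded after 24 hours, so most of an in-hospital window would run unblinded.

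Thromboembolism is the main named risk of the product. A significant excess of it also halts enrollment under Stopping Criteria, so the counting rule bears on a trial decision as well as on the final table.

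**Working it through.** The plan states no event rate, length of stay or power for safety, so there is no figure of its own to reproduce. The check has a textual part and an illustrative part.

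**1. The sections side by side**

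| Question | One answer | Other answer |
|---|---|---|
| When does adverse event collection end? | Discharge (Endpoints; Patient Assessment) | 60 ± 14 days (Schedule of Events; Transition) |
| What does the hospital-stay limit cover? | Possibly the whole list (Endpoints) | Allergic reactions only (Patient Assessment) |
| Is infection followed after discharge? | Yes, by contact with parents (Transition) | Nothing additional (Protection against risks) |
| Do component events learned at the call count? | Not stated | Not stated |

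**2. The call window.** 60 − 14 = 46 and 60 + 14 = 74, so a call may fall anywhere from day 46 to day 74 after the end of the treatment period. Every permitted call covers the first 46 days. Follow-up to the call itself can differ between children by up to 74 − 46 = 28 days.

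**3. Effect of a shorter stay at equal true risk.** All stays and onset patterns here are assumed. One arm's stay shortens from L0 to L1 days.

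- *Constant hazard:* expected events are proportional to time observed, so the loss is 1 − L1/L0.
  - 15 to 12 days: 1 − 12/15 = 20%.
  - 15 to 10 days: 1 − 10/15 = 33%.
- *Early onset:* onset times are exponential with mean m, so the loss is 1 − [1 − exp(−L1/m)] / [1 − exp(−L0/m)].
  - 15 to 12 days, m = 3: 1 − 0.982/0.993 = about 1%.
  - 15 to 12 days, m = 5: 1 − 0.909/0.950 = about 4%.
  - 15 to 10 days, m = 3: 1 − 0.964/0.993 = about 3%.
  - 15 to 10 days, m = 5: 1 − 0.865/0.950 = about 9%.

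The answer runs from about 1% to 33%, depending almost entirely on inputs that the documents do not give.

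**4. The same effect on proportions.** Fisher's test compares children with and without an event. With P = 1 − exp(−hazard × days), equal hazards of 0.005, 0.01 and 0.02 per day, and stays of 10 versus 14 days, the proportions are 4.9% v 6.8%, 9.5% v 13.1% and 18.1% v 24.4%. The spurious risk ratio is 0.72 to 0.74. With one common window it is 1.0.

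**5. Why a single event can matter.** With the planned 15 per arm and no events on placebo, two-sided Fisher p-values are:

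- 4 v 0: 2 × C(15,4)/C(30,4) = 2 × 1365/27405 = 0.0996.
- 5 v 0: 2 × C(15,5)/C(30,5) = 2 × 3003/142506 = 0.042.

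Counting or not counting one post-discharge event can therefore move the comparison across the 0.05 line.

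**The case against.** The strongest defence is that little is lost. The product is given as one infusion. Allergic reaction is assessed at administration, and respiratory failure is defined as reintubation after extubation, so many events should fall well before discharge. With onset that early, the loss is the 1–9% computed above. Even a 20% loss applied to 3 expected events in an arm of 15 (assumed) removes only 3 × 0.20 = 0.6 of an event. An actively examined in-hospital window, with call-based events reported apart, would be a defensible design. The two statements on infection can also be read together as no extra testing but contact with parents. All of this stands as a limit on size. None of it tells the reader which window the plan uses.

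A reader might infer more than the documents support:

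- *That the whole primary safety endpoint is confined to the hospital stay.* Infection carries no such limit in Endpoints and is followed by parent contact.
- *That infection is practically unobservable under the plan.* The remark on latency contrasts infection with the 24-hour treatment period, not with discharge, and later contact is provided.
- *That the bias is 20–33%.* That needs constant hazard and assumed stays.
- *That running the window to the call makes it fixed and cures the problem.* The call date varies by up to 28 days. Post-discharge time also rests on parental recall, against 8-hourly assessment with Doppler confirmation in hospital.
- *That readmissions should count.* Hospitalization is not a component of the endpoint.

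**Conclusion.** The point holds as an internal contradiction with a missing counting rule, and this needs no assumption. Sections disagree on when adverse event collection ends, on the reach of the hospital-stay limit and on infection surveillance. None says whether component events learned at the call enter the primary safety endpoint.

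If discharge is the intended end, the window length is a post-randomization outcome that the planned test ignores. The direction of the resulting bias is clear only if stay differs between arms and events continue to near or beyond discharge, and the documents give no data on either. For an assumed shortening from 15 to 10–12 days, the loss is about 1–9% of events with early onset (mean 3 to 5 days) and 20–33% at constant hazard. These are illustrations, not estimates.

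A common window does not make 15 per arm adequate for safety inference. At an assumed true hazard ratio of 2 and placebo hazards of 0.005 to 0.02 per day, exact power over 46 days is only about 8% to 18%.

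**What to change.** 1. Reconcile Endpoints, Patient Assessment, the Schedule of Events, Transition From Research Participation and Protection against risks, so that they give one account of the adverse event window and of infection surveillance.
2. Count the existing components, by onset date, from study-drug infusion to one common cut-off day that every call covers. An example is 46 days after the end of the treatment period, the earliest permitted call. The call must then record an onset date for each event.
3. State that component events learned at the call count if their onset is on or before the cut-off.
4. Report in-hospital events (examined, with Doppler confirmation of thromboembolism) and post-discharge events (parent-reported) separately as well as combined, by arm.
5. List hospitalizations, and any infections reported after the cut-off, descriptively. Do not add them as endpoint components.

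The cost is mainly wording plus an onset date on the call form, since the call is already planned for every subject. The downside is weaker ascertainment after discharge. A shorter stay still moves more of the window into parent report, so dependence on length of stay is reduced but not removed. Infections that take months to appear may still be missed.
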